7.7. Baseline Characteristics

Patient age in years on the date of randomization will be calculated by dividing the number of days since birth (Day 1) by 365.25. If body surface area (BSA) expressed in m² is missing in the study database, then it will be calculated using the formula⁵

$$BSA = \sqrt{\frac{W \times H}{3600}}$$

where W is the patient's weight in kg and H is the patient's height in cm.

Summaries of baseline characteristics will include within- and between-treatment-arm descriptive statistics appropriate for continuous, time-to-event and categorical variables (see section 7). Separate summaries will be produced for the ITT, safety, response-available, per-protocol and crossover patient populations. The Student t test (continuous variables), the log rank test (time-to-event variables), or the Fisher exact test (categorical variables) will be used to quantify the effectiveness of randomization to create similar distributions of these variables between treatment arms. The effect any baseline characteristic with two-sided p -value <0.10 has on efficacy outcomes will be investigated (see sections 7.9.1 through 7.9.6).

Baseline characteristics include demographic data (e.g., age, sex, race, ethnicity, height, weight and BSA); AML history (e.g., clinical onset of AML [de novo AML, prior MDS or prior leukemogenic therapy], time since AML diagnosis, peripheral blood and bone marrow blast percentages, cytogenetic risk group, frontline AML therapy and response to frontline AML therapy [see section 6]); MCL-1 dependence; and other

medical history (e.g., baseline ECOG performance status, hemoglobin, leukocyte and platelet counts, and blood chemistry parameters assessing liver and kidney function). Reported medical history terms will be mapped to Medical Dictionary for Regulatory Activities (MedDRA) preferred terminology and then summarized within and between treatment-arms by incidence rates for each MedDRA primary system organ class (SOC) and preferred term (PT). Optionally, depending on the perceived relevance, prestudy medications will be mapped to terminology in the World Health Organization (WHO) Drug Dictionary Enhanced (DDE) and then summarized within treatment arm by usage rates for each WHO DDE anatomical and therapeutic class (ATC) and preferred (i.e., standardized) drug name. Relevant data supporting these summaries will be listed by patient within treatment arm.

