Analysis Population	Analytical Method	Response Assessment	Role of Analysis
Intent-to-Treat	Logistic regression	Central	Supportive
Intent-to-Treat	Logistic regression	Local and Sponsor	Supportive
Per-Protocol	Stratified CMH	Central	Supportive
Per-Protocol	Stratified CMH	Local and Sponsor	Supportive
Per-Protocol	Logistic regression	Central	Supportive
Per-Protocol	Logistic regression	Local and Sponsor	Supportive
Response-Available	Logistic regression	Central	Supportive
Response-Available	Logistic regression	Local and Sponsor	Supportive
Subgroups based on patient characteristics	Logistic regression	Central, Local and Sponsor	Exploratory

If the test for between-treatment-arm homogeneity of any baseline characteristic gives two-sided p-value <0.10, then the effect that baseline characteristic has on cycle-1 CR rate will be quantified using LR. Two LR models will be fit. One model will include the baseline characteristic in question as the only independent variable, and the second model will include the baseline characteristic and the stratification factors used for randomization.

Other remission rates (e.g., cycle-1 combined CR rate and cycle-1 combined remission rate) will be summarized similar to cycle-1 CR rate.

Correlation between central and local review will be assessed descriptively in 2-way frequency tables, both as a bivariate response (CR yes or no) and on the full scale (CR, CRi, CRp, PR, resistance/relapse). The simple kappa coefficient^{8,9} will be calculated as a measure of agreement between the central and local reviews. Since the two response variables are two independent ratings of the same tissue sample, the kappa coefficient equals 1 when there is complete agreement of the raters. When the observed agreement exceeds chance agreement, kappa is positive, with its magnitude reflecting the strength of agreement. Although this is unusual in practice, kappa is negative when the observed agreement is less than chance agreement.⁸

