Hypothesis testing for PFS will be based on the stratified log rank test statistic (see Table 6). Stratification levels will be the same as those used for the randomization scheme (see section 6). Two Cox proportional hazards (PH) models will be fit to provide estimates of the hazards ratio (HR). One model will include treatment arm as the only independent variable, and the second model will include treatment arm and the stratification factors used for randomization. Kaplan-Meier (KM) “survival” curves¹⁰ will be graphed for visual inspection of differences in PFS between the treatment arms. Within-treatment-arm statistics will include the number and percentage of censored PFS times, quartile PFS times, 95% CIs for the quartile PFS times, and KM “survival” percentages with 95% CIs at select milestone times (e.g., 6, 12 and 18 months). Between-treatment-arm statistics will include HRs from the Cox PH models and their 95% CIs.

Sensitivity analyses will be run with PFS time censored on the date of stem cell transplantation (bone marrow [BM] or peripheral blood stem cells [PBSC]).

Table 6. Statistical Analyses of PFS, OS, RFS and CR Duration

Analysis Population	Analytical Method	Censor for Transplant	Role of Analysis
Intent-to-Treat	Stratified log rank	No	Primary
Intent-to-Treat	Stratified log rank	Yes	Supportive
Intent-to-Treat	Cox PH Model	No	Supportive
Intent-to-Treat	Cox PH Model	Yes	Supportive
Per-Protocol	Stratified log rank	No	Supportive
Per-Protocol	Stratified log rank	Yes	Supportive
Per-Protocol	Cox PH Model	No	Supportive
Per-Protocol	Cox PH Model	Yes	Supportive
Subgroups based on patient characteristics	Cox PH model	No	Exploratory

If the test for between–treatment-arm homogeneity of any baseline characteristic gives two-sided p-value <0.10, then the effect that baseline characteristic has on PFS time will be quantified using Cox PH modeling. Two PH models will be fit. One model will include the baseline characteristic in question as the only independent variable, and the second model will include the baseline characteristic and the stratification factors used for randomization.

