7.9.3. Stem Cell Transplant Rate

Stem cell transplant (SCT) rate is the percentage of patients proceeding to SCT within 90 days after their last dose of study drug regardless of whether the patient remains enrolled in this study. Unless documentation of SCT is provided, patients who are lost to follow-up within the 90 days following their last dose of study drug are counted among those not receiving SCT.

Hypothesis testing will be based on the stratified CMH general association test statistic (see Table 7). Stratification levels will be the same as those used for the randomization scheme (see section 6).

Within–treatment-arm statistics will include the number and percentage of patients counted as not receiving SCT due to being lost to follow-up; proportion of patients receiving SCT within 90 days after their last dose of study drug; and exact 95% CI estimated without stratification. Between–treatment-arm statistics will include the Mantel-Haenszel odds ratio and 95% CI estimated with stratification.

Table 7. Statistical Analyses of Stem Cell Transplant Rate

Analysis Population	Analytical Method	Role of Analysis
Intent-to-Treat	Stratified CMH	Primary
Per-Protocol	Stratified CMH	Supportive
Subgroups based on patient characteristics	Logistic regression	Exploratory

If the test for between–treatment-arm homogeneity of any baseline characteristic gives two-sided p-value <0.10, then the effect that baseline characteristic has on SCT rate will be quantified using LR. Two LR models will be fit. One model will include the baseline characteristic in question as the only independent variable, and the second model will include the baseline characteristic and the stratification factors used for randomization.

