7.9.4. Overall Survival

OS time is defined for all patients and is measured from the date of randomization (Day 1) until death from any cause.

Rules for censoring OS time are:

- A patient with OS continuing as of the date he is lost to follow-up will have his OS time censored on the date of his last assessment of any type
- A patient with OS continuing as of the database lock will have his OS time censored on the date of his last assessment of any type

Hypothesis testing for OS will be based on the stratified log rank test statistic (see Table 6). Stratification levels will be the same as those used for the randomization scheme (see section 6). Two Cox PH models will be fit to provide estimates of the HR. One model will include treatment arm as the only independent variable, and the second model will include treatment arm and the stratification factors used for randomization. KM survival curves will be graphed for visual inspection of differences in OS between the treatment arms. Within-treatment-arm statistics will include the number and percentage of censored OS times, quartile OS times, 95% CIs for the quartile OS times, and KM survival percentages with 95% CIs at select milestone times (e.g., 6, 12 and 18 months). Between-treatment-arm statistics will include HRs from the Cox PH models and their 95% CIs.

Sensitivity analyses will be run with OS time censored on the date of BM or PBSC transplant.

If the test for between-treatment-arm homogeneity of any baseline characteristic gives two-sided p-value <0.10, then the effect that baseline characteristic has on OS time will be quantified using Cox PH modeling. Two PH models will be fit. One model will include the baseline characteristic in question as the only independent variable, and the second model will include the baseline characteristic and the stratification factors used for randomization.

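### The SAP's models for an imbalanced baseline characteristic omit treatment arm, so they confound the characteristic's effect if the arms differ and give no adjusted ACM-CM estimate

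*SAP*

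**What the plan says.** SAP 7.7 tests each baseline characteristic between arms (t test, log-rank or Fisher exact). For any with two-sided p below 0.10, it says that the effect the characteristic "has on efficacy outcomes will be investigated".

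SAP 7.9.1 gives the detail for cycle-1 CR. The trigger is that the test for between-arm "homogeneity of any baseline characteristic gives two-sided p-value <0.10". The target is the effect that the "baseline characteristic has on cycle-1 CR rate will be quantified using LR". Two logistic models follow: "One model will include the baseline characteristic in question as the only independent variable, and the second model will include the baseline characteristic" together with the randomisation strata. Under SAP section 6 the only stratification factor is response to first-line therapy, in three categories.

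The same pair of models is repeated for the other endpoints:
- PFS (7.9.2): "the effect that baseline characteristic has on PFS time will be quantified using Cox PH modeling"
- Stem cell transplant rate (7.9.3): "the effect that baseline characteristic has on SCT rate will be quantified using LR"
- OS (7.9.4): "the effect that baseline characteristic has on OS time will be quantified using Cox PH modeling"
- RFS (7.9.5) and CR duration (7.9.6), in matching terms.

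Treatment arm cannot be taken as implied. Where the SAP wants it in a model it names it, as in the main Cox models of 7.9.2 and the MCL-1 dependence model of 7.9.1.

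**The concern.** Two things follow from leaving arm out.

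1. **The stated target is confounded.** The rule fires only when a characteristic is associated with arm, and the design assumes that arm is strongly associated with CR. In a model without arm, the characteristic acts as a proxy for treatment. The strata in the second model do not cure this: stratified randomisation balances them across arms, so they carry little information about which arm a patient was in.
2. **The rule gives no adjusted treatment comparison.** An imbalance between arms naturally raises the question of whether it contributes to the observed ACM-CM difference. A model with no arm term cannot answer that.

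The study report could therefore present a prognostic effect that is really a treatment effect, or hide a real one, without showing how the treatment estimate behaves once the imbalance is taken into account.

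**Working it through.** **Inputs.** Protocol 11.2.2: 28 per arm, CR 70% vs 30%, one-sided 2.5%, 90% power. SAP 5.1.2: 53 per arm, 70% vs 40%, one O'Brien-Fleming interim analysis, 90% power. Trigger: p below 0.10, with Fisher's test for categorical characteristics (SAP 7.7). The documents give no distribution for any characteristic, so a binary characteristic X is assumed.

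**Design figures.** The point does not rest on them, but they supply the rates and arm sizes. With unpooled variance, n = (1.960 + 1.282)² × (0.21 + 0.21) / 0.40² = 27.6, so 28 per arm, with power 90.4%. The SAP boundaries 0.00321 and 0.02378 at information fraction 56/106 give overall alpha 0.0250 and power 90.0%. Both designs reproduce.

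**Expected counts, X with no effect within either arm.**
1. At 28 per arm, the smallest symmetric imbalance that fires the rule is 18/28 on ACM vs 10/28 on CM (Fisher p = 0.060).
2. Expected CRs with X: 18 × 0.7 + 10 × 0.3 = 15.6 of 28. Without X: 10 × 0.7 + 18 × 0.3 = 12.4 of 28.
3. Odds ratio for X without arm: (15.6/12.4) / (12.4/15.6) = 1.58. The true value is 1.00.
4. With arm added, the model returns 1.00 for X and (0.7/0.3) / (0.3/0.7) = 5.44 for ACM vs CM.
5. SAP design, 32/53 vs 21/53 (p = 0.052). With X: 32 × 0.7 + 21 × 0.4 = 30.8 of 53. Without X: 21 × 0.7 + 32 × 0.4 = 27.5 of 53. Odds ratio: (30.8/22.2) / (27.5/25.5) = 1.29.
6. With equal CR rates in the two arms, the same calculation gives exactly 1.00.

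**Expected counts, X with a real effect.** Take a within-arm odds ratio of 0.50, with 70% and 30% as the CR rates in patients without X. At 18/28 vs 10/28 the model without arm shows 0.87. At 20/28 vs 8/28 it shows 1.09, which reverses the direction. With arm added, 0.50 is recovered (fitted for the 18/28 vs 10/28 case).

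**Simulation.** X is Bernoulli(0.5) with no effect on CR, kept only if Fisher p is below 0.10 and oriented so that it is commoner on ACM. Logistic models were fitted with and without arm. Repeated runs at 28 per arm and 70% vs 30% agreed closely.

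| Design | Median OR for X, no arm | Wald p<0.05, no arm | Median OR, arm added | Wald p<0.05, arm added |
|---|---|---|---|---|
| 28 per arm, 70% vs 30% | 1.67 to 1.7 | about 13% | 0.96 to 0.97 | 3 to 4% |
| 53 per arm, 70% vs 40% | 1.31 | 9% | 1.00 | about 6% |
| 28 per arm, 50% vs 30% | 1.35 | 6% | not recorded | 5% |

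**What an imbalance can do to the ACM-CM estimate.** Suppose there is no treatment effect, CR is 30% without X, and X has odds ratio 2. At 18/28 vs 10/28 the expected CR rates are 40.4% and 35.8%, a crude ACM-CM odds ratio of 1.22. With odds ratio 4 for X it is 1.47. The triggered models have no term that would show this.

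**How often the rule fires.** In the simulation a binary characteristic triggered about 5% of the time. If 10 to 20 such characteristics are tested and are independent (an assumption), the chance of at least one trigger is 1 − 0.95^10 = 40% to 1 − 0.95^20 = 64%.

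**The case against.** Several points on the other side are sound.

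- **Inference is untouched.** The primary analyses are the ITT stratified CMH and log-rank tests, and SAP 7.5.2 lets only the primary-analysis p-value decide significance. A reader might infer that the trial's main comparison is biased. The documents do not support that.
- **The SAP promises only the characteristic's effect.** It nowhere says that these models adjust the ACM-CM comparison. That weakens the second half of the concern but not the first, because the promised quantity is the one that is confounded.
- **The plan is not silent on adjustment.** A reader might infer that no baseline factor is ever taken into account. In fact, response to first-line therapy is handled by stratified randomisation, the stratified tests, the Mantel-Haenszel odds ratio, and Cox models with arm plus strata. MCL-1 dependence has a logistic model with arm and interaction in 7.9.1, and the other remission rates are summarised similarly. Exploratory subgroup analyses are listed in Tables 5 to 7 without stated covariates. None of this is a general adjusted model for age, cytogenetic risk, blast percentage and the rest.
- **The size is conditional.** The 1.7 figure uses the protocol's arm sizes and rates, whereas the SAP that contains the rule plans 53 per arm and a smaller difference. Orienting X towards ACM fixes the direction of the bias; without that convention the error falls on either side of 1.
- **Selection by a baseline significance test remains** even after arm is added. That is a fair criticism of the rule, but a separate one.

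**Conclusion.** The omission is real and worth correcting before database lock, as a defect in supportive analyses only. If ACM and CM differ in outcome, the triggered models misstate the effect of the imbalanced characteristic. For an inert binary characteristic the median odds ratio is about 1.7 under the protocol's assumptions and about 1.3 under the SAP's. The error shrinks with the treatment difference and vanishes if the arms have equal CR rates. These figures rest on an assumed binary characteristic with 50% prevalence and on each document's assumed CR rates. They were worked out for CR only: the same mechanism applies to the other endpoints, but its size there was not calculated.

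The rule also provides no ACM-CM estimate adjusted for the characteristic that triggered it. This is a gap in the rule and not a complete absence of adjustment in the plan, given the provisions for MCL-1 dependence and response to first-line therapy. The conclusion does not depend on which document's Stage 2 sample size applies.

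**What to change.** In SAP 7.9.1 to 7.9.6, add treatment arm to both triggered models: (a) arm + characteristic; (b) arm + characteristic + randomisation strata. From each, report the ACM-CM odds ratio (7.9.1, 7.9.3) or hazard ratio (7.9.2, 7.9.4 to 7.9.6) with its 95% CI beside the primary estimate, labelled supportive. The characteristic's own effect can be reported from the same fit.

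The cost is one phrase in each of six subsections. No new data are needed, and there is no effect on the type-1 error rate because supportive results do not enter the testing hierarchy. The downside is small: model (b) will be imprecise at these sample sizes, most of all for RFS and CR duration, which include responders only. The intervals should be read with that in mind.

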7.9.2. Progression-Free Survival

PFS time is defined for all patients and is measured from the date of randomization (Day 1) until (a) treatment failure, (b) relapse after combined remission, or (c) death from any cause, whichever occurs first.

Treatment failure is defined as failing to achieve a combined remission following induction therapy. The date of treatment failure is the protocol-specified date for bone marrow collection following the first induction attempt (i.e., at neutrophil and platelet recovery or Day 45 of the treatment cycle, whichever occurs first), regardless of whether the patient received a second induction attempt (unless the second induction resulted in a combined remission in which case “treatment failure” does not apply).

Additional rules for defining PFS time are:

- A patient found to have relapsed after missing one or more scheduled response assessments will have his PFS time end on the scheduled date for the first missed response assessment following the last confirmation of combined remission
- A patient who misses the first scheduled response assessment and who never achieves combined remission will have his PFS time end on the scheduled date for the first response assessment (unless the patient died before this date)

Rules for censoring PFS time are:

- A patient with PFS continuing as of the date he is lost to follow-up will have his PFS time censored on the date of his last response assessment
- A patient with PFS continuing as of the database lock will have his PFS time censored on the date of his last response assessment

Hypothesis testing for PFS will be based on the stratified log rank test statistic (see Table 6). Stratification levels will be the same as those used for the randomization scheme (see section 6). Two Cox proportional hazards (PH) models will be fit to provide estimates of the hazards ratio (HR). One model will include treatment arm as the only independent variable, and the second model will include treatment arm and the stratification factors used for randomization. Kaplan-Meier (KM) “survival” curves¹⁰ will be graphed for visual inspection of differences in PFS between the treatment arms. Within-treatment-arm statistics will include the number and percentage of censored PFS times, quartile PFS times, 95% CIs for the quartile PFS times, and KM “survival” percentages with 95% CIs at select milestone times (e.g., 6, 12 and 18 months). Between-treatment-arm statistics will include HRs from the Cox PH models and their 95% CIs.

Sensitivity analyses will be run with PFS time censored on the date of stem cell transplantation (bone marrow [BM] or peripheral blood stem cells [PBSC]).

Table 6. Statistical Analyses of PFS, OS, RFS and CR Duration

Analysis Population	Analytical Method	Censor for Transplant	Role of Analysis
Intent-to-Treat	Stratified log rank	No	Primary
Intent-to-Treat	Stratified log rank	Yes	Supportive
Intent-to-Treat	Cox PH Model	No	Supportive
Intent-to-Treat	Cox PH Model	Yes	Supportive
Per-Protocol	Stratified log rank	No	Supportive
Per-Protocol	Stratified log rank	Yes	Supportive
Per-Protocol	Cox PH Model	No	Supportive
Per-Protocol	Cox PH Model	Yes	Supportive
Subgroups based on patient characteristics	Cox PH model	No	Exploratory

If the test for between–treatment-arm homogeneity of any baseline characteristic gives two-sided p-value <0.10, then the effect that baseline characteristic has on PFS time will be quantified using Cox PH modeling. Two PH models will be fit. One model will include the baseline characteristic in question as the only independent variable, and the second model will include the baseline characteristic and the stratification factors used for randomization.

